4.0 SUBJECT SCREENING AND REGISTRATION PROCEDURES

Patient registration for this trial will be centrally managed by the Coordinating Center of The University of Michigan Rogel Cancer Center as described below:

A potential study subject who has been screened for the trial and who has signed the Informed Consent document will be initially documented by the participating site on a Screening and Enrollment Log.

It is the responsibility of the local site investigator to determine patient eligibility prior to submitting patient registration request to the Coordinating Center. After patient eligibility has been determined, a copy of the completed Eligibility Worksheet together with all the pertinent de-identified source documents will be submitted by the requesting site to the Coordinating Center, by email to [contact].

The Multi-Site Coordinator (MSC) of the Coordinating Center will review the submitted documents and process the registration. Sites should inform the Multi-Site Coordinator of a potential registration by 5 p.m. on the day prior to registration. Same day registrations cannot be guaranteed.

An email will be sent by the MSC to the requesting site registrar to confirm patient registration and to provide the study identification number that has been assigned to the patient. In addition, a copy of the completed Eligibility Worksheet signed and dated by the MSC, will be sent back to the requesting site registrar.

Patients found to be ineligible for participation after being consented will be considered screen failures, and documented as such in a Screening and Enrollment Log. These patients will not have study identification number assigned to them, and will not receive study treatment.

5.0 TREATMENT PLAN

5.1 Treatment Dosage and Administration

Protocol treatment must start within 14 business days of enrollment to the study.

There are 2 cohorts for accrual with Cohort A being accrued first. Cohort B will follow and will have 2 stages of accrual. Cohort A will accrue 11 patients to ESK981 monotherapy treatment. Then Cohort B (combination therapy) will begin accrual of 17 patients to the first stage and if the interim analysis permits, the second stage will accrue an additional 19 patients.

5.1.1 Therapy with ESK981 will include starting dose of 160 mg (4 capsules) PO daily for 5 consecutive days followed by a 2-day off drug in each week, repeated weekly in 28 day cycles. Patients will continue treatment until disease progression or intolerable toxicity.

REGIMENT DESCRIPTION					
Agent	Premedications; Precautions	Dose	Route	Schedule	Cycle Length
ESK981	n/a	160 mg	PO	Once daily for 5 consecutive days of every week (5 days on followed by 2 days off)	28 days
Nivolumab (solution for injection)	Per institutional guidelines, none mandated.	480 mg/dose	IV infusion over 30-60 minutes with a sterile, nonpyrogenic, low protein binding 0.2 to 1.2 micrometer in-line filter. Follow with saline flush.	Day 1	28 days

Dose Level	Dose of ESK981	Dose of Nivolumab
Level 0	160 mg	Fixed at 480 mg flat dose
Level -1	120 mg	Fixed at 480 mg flat dose
Level -2	80 mg	Fixed at 480 mg flat dose

Dose-Limiting Toxicity (DLT)

Dose limiting toxicity (DLT) will be defined as any Grade 3 or higher toxicity (as defined by CTCAE 4.03) that occurs during the DLT evaluation period (Cycle 1 i.e. 28 days) EXCEPT laboratory abnormalities that are not clinically relevant or significant.

Subjects will be given a pill diary and instructed to complete it every cycle. Doses missed by 6 or more hours or vomited will be skipped and not made up but will be recorded on the diary as missed or vomited. The subject will be advised not to take any additional doses, but to wait for the next scheduled dose.

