6.0 SCHEDULE OF ASSESSMENTS

6.1 Time and Events Table

1 cycle (C) = 28 days (D).

Trial Period	Screening (-28 to -1 days)	C1D1	C2D1	C3D1	C4D1	Additional Cycles...	EOT ⁷	Follow-Up ⁸
							30 days from last dose (+/- 7 business days)	Every 12 weeks (+/-14 business days) for up to 24 months/death
Informed Consent	X							
Tumor tissue specimen (15 FFPE slides required; blocks preferred) identified	X							
Blood for banking		X						
History, PE, Concomitant Meds, Vital Signs ¹	X	X	X	X	X	X	X	
PT/INR, aPTT	X							
Karnofsky Performance Status	X	X	X	X	X	X	X	
Pregnancy Test for WOCBP ²	X							
Toxicity (include DLT) Evaluations ¹²	X	X	X	X	X	X	X	
CBC with differential, platelets ³	X	X ¹³	X ¹³	X	X	X	X	
COMP ⁴	X	X	X	X	X	X	X	
TSH	X	Every 12 weeks from Cycle 1 Day 1 ⁵						
QoL (EQ-5D-5L)		X	X	X		X ¹⁴		X
Pill Diary collection/handing out		X	X	X	X	X		
Tumor response assessment ⁶ (CT chest, CT or MRI abdomen/pelvis; CT or MRI brain if clinically indicated)	X			X		X ⁶		X
Treatment								
ESK98 ^{9, 10} (Cohort A and B)		X	X	X	X	X		
Nivolumab ¹¹ (Cohort B only)		X	X	X	X	X		
Survival Status								X

1. Vital signs will include weight, temperature, pulse, respirations, blood pressure; height will be obtained at screening only.
2. WOCBP: Women of child bearing potential; either urine or serum pregnancy test.
3. CBC with diff includes total WBC, hemoglobin, hematocrit and differential of the WBC including absolute counts. Other checks are at discretion of treating investigator.

4. COMP or Comprehensive metabolic profile includes sodium, potassium, chloride, bicarbonate, BUN, creatinine, AST, ALT, alkaline phosphatase, total bilirubin.
5. TSH: Every 12 weeks from Cycle 1 Day 1 (i.e. Cycle 4 Day 1; Cycle 7 Day 1, etc.).
6. Window of +/- 7 business days. Imaging will be with or without intravenous contrast, before or on associated visit. CT or MRI brain with (preferred) or without IV contrast if suspected or known brain metastases. Frequency of tumor assessments will be q2 cycles (i.e. q 8 weeks) for first 4 assessments beyond baseline and then q 3 cycles (i.e. 12 weeks) subsequently until withdrawal of consent/death/2 years from C1 D1 whichever is later. If CR/PD, should be confirmed with repeat imaging after an interval of at least 4 weeks. In follow-up, if subjects are on alternative therapies, no mandated imaging but data from routine imaging will be captured at least every 12 weeks if available (+/- 7 business days).

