7. End of treatment visit may or may not be the same day as a planned study visit. If it is not on a planned study visit, the minimum assessments listed in the schedule must be completed.
8. Follow-up may be conducted by phone call or a clinic visit.
9. Study drug(s) must be started within 14 business days from time of enrollment.
10. ESK981 will only be given on days 1-5 of each week of each treatment cycle followed by 2 days off.
11. Nivolumab will be administered on Day 1 of each treatment cycle in Cohort B.
12. All Serious Adverse Events (SAEs) occurring from the initial study treatment administration through 60 days following the last dose of the study treatment should be reported to the Coordinating Center. Any SAEs occurring after 60 days following the last dose of the study treatment that are believed to be related to study drug should also be reported to the Coordinating Center.
13. CBC with diff must be obtained weekly during Cycles 1 and 2. For patients who experience no \geq Grade 3 hematological toxicity during Cycles 1 and 2, monthly blood counts will be obtained during subsequent cycles.
14. QOL obtained Cycles 1-3, 5, 7 and 9 then q 3 cycles (12 weeks) subsequently

NOTE:

All assessments have a window of \pm 3 business days unless otherwise mentioned.

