- **Serious Adverse Events** Serious adverse events (SAEs) occurred were deemed unlikely or not related to ESK981. Three patients (1 patient in the 97.4 mg/m² cohort and two patients in the 126.6 mg/m² cohort) experienced SAEs that were categorized as possibly or definitely related to ESK981: pyrexia, hemolytic anemia, hyperbilirubinemia, dyspnea, neutropenia, ECG change, and chest discomfort. There were no deaths occurred during the study.
- **Procedure in case of Pregnancy** The effect of ESK981 in pregnant and lactating women is not known, and the exposure of a fetus or nursing infant is considered a potential risk. ESK981 can cause fetal harm when administered to a pregnant woman based on its mechanism of action. Subjects receiving ESK981 are advised to use two acceptable methods of birth control (one of which must include a condom as a barrier method of contraception) starting at the time of screening for an ESK981 study and continuing throughout the course of treatment and for at least six months after ESK981 is discontinued.

If during the conduct of the clinical trial, a male subject impregnates his partner, the subject should report the pregnancy to the investigator. The investigator should report the pregnancy to the Coordinating Center as an SAE within 24 hours of awareness of the event. The expected date of delivery or expected date of the end

of the pregnancy, last menstruation, estimated fertility date, pregnancy result and neonatal data etc., should be included in this information.

The investigator should report the outcome of the pregnancy (independent of outcome, e.g., full term delivery, pre-term delivery, spontaneous abortion, induced abortion, stillbirth, death of newborn, congenital anomaly [including anomaly in a miscarried fetus, etc.] in accordance with the same reporting procedure as for SAEs. The date of outcome of the pregnancy, gestational age, date of birth and neonatal data etc., should be included in this information.

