11.3 Early Stopping Due to Toxicity

Toxicity will be assessed in each cohort. If the DLT proportion is >30% during cycle 1 in Cohort A then dosing as is planned for the combination cohort will require modification before Cohort B can begin. Accrual of Cohort B will not begin until toxicity assessment of Cohort A is complete.

Cohort B will assess DLT proportions in the first 6 patients. If 2 or more DLTs occur in the first 6 patients of Cohort B, then dosing in the combination treatment in Cohort B will be decreased one dose level. If a decreased dose level is opened, assessment of another 6 patients will be assess for DLTs; if 2 or more DLTs occur then the trial will be halted. Accrual will be held during toxicity evaluation.

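### No post-dose chemistry panel is required within the 28-day DLT window, and the plan does not say whether a result first seen at C2D1 counts as a Cycle 1 DLT

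*Combined protocol and SAP*

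**What the plan says.** Section 5.1 defines a DLT as a toxicity of Grade 3 or higher "that occurs during the DLT evaluation period (Cycle 1 i.e. 28 days", and then makes an exception: "EXCEPT laboratory abnormalities that are not clinically relevant or significant". Section 5.2 says toxicity is assessed according to the Time and Events Table, so that table sets what the DLT count can see.

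In that table (section 6.1):

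- A cycle is 28 days, so C2D1 is nominally day 29.
- The chemistry row (COMP) is marked at screening, C1D1, C2D1 and later cycles, with no weekly requirement. Footnote 4 gives its content: "COMP or Comprehensive metabolic profile includes sodium, potassium, chloride, bicarbonate, BUN, creatinine, AST, ALT, alkaline phosphatase, total bilirubin".
- The toxicity row, which includes DLTs, is marked on C1D1 and next on C2D1.
- Footnote 13 tightens the blood count only: "CBC with diff must be obtained weekly during Cycles 1 and 2".
- Footnote 10 sets the dosing days: "ESK981 will only be given on days 1-5 of each week of each treatment cycle followed by 2 days off".
- Assessments carry a window of ±3 business days unless another is stated. COMP has no window of its own.

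Section 11.3 rests its numeric rules on the Cycle 1 DLT count. A DLT proportion above 30% in Cohort A requires the planned combination dosing to be modified before Cohort B opens. "If 2 or more DLTs occur in the first 6 patients of Cohort B", the dose goes down one level and another six patients are assessed; 2 or more DLTs there halt the trial. Accrual is held during the toxicity evaluation.

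**The concern.** The DLT definition admits clinically relevant laboratory toxicity of Grade 3 or higher, but the schedule requires no chemistry sample between the first dose and the end of the window. The C1D1 panel is in practice a baseline value. The next one falls nominally one day after the window closes and after two days off ESK981.

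Two things could go wrong. An asymptomatic but clinically relevant abnormality could arise and settle before anyone draws a sample. Or one present at C2D1 could be counted for a patient whose visit was brought forward to day 28 or earlier, and not for a patient seen on day 29 or later, because the plan has no attribution rule.

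Chemistry is relevant for this drug. Sections 1.2.4 and 8.1.2 list the serious events judged possibly or definitely related to ESK981 in phase 1 as "pyrexia, hemolytic anemia, hyperbilirubinemia, dyspnea, neutropenia, ECG change, and chest discomfort". Hyperbilirubinemia is a finding that COMP would show and a CBC would not. At stake is whether the counts that open Cohort B and clear the first six combination patients reflect all the toxicity that the definition covers.

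**Working it through.** The documents state no operating characteristic for either toxicity gate, so there is no figure of the plan's own to reproduce. The check has three parts.

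**1. Day count.** Dosing on days 1–5 of each week (footnote 10) gives days 1–5, 8–12, 15–19 and 22–26. The last Cycle 1 dose is day 26. C2D1 is 28 + 1 = day 29, so the gap is 29 − 26 = 3 days, about 72 h. Required post-baseline chemistry panels with a nominal date on days 2–28: none.

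**2. Visit window.** Moving C2D1 by 3 business days, ignoring public holidays:

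| C1D1 weekday | Earliest C2D1 draw | Latest C2D1 draw |
|---|---|---|
| Mon, Tue | day 24 | day 32 |
| Wed | day 24 | day 34 |
| Thu, Fri | day 26 | day 34 |

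So the first post-dose panel may fall inside the DLT window, even on a dosing day (24 and 26 both lie in 22–26), or up to 34 − 28 = 6 days after it.

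**3. Sensitivity of the gates to missed DLTs.** With 11 patients in Cohort A, 3/11 = 27% and 4/11 = 36%, so above 30% means 4 or more. Let p be the counted DLT rate.

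- Cohort B gate: P(X ≥ 2 | n = 6) = 1 − (1 − p)^6 − 6p(1 − p)^5.
  - p = 0.35: 1 − 0.0754 − 0.2437 = 0.681.
  - p = 0.25: 1 − 0.1780 − 0.3560 = 0.466.
- Cohort A gate: P(X ≥ 4 | n = 11) = 1 − Σ C(11,k) p^k (1 − p)^(11−k), k = 0 to 3.
  - p = 0.40: 0.704.
  - p = 0.30: 0.430.

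In general, if the true rate is t and a share f goes uncounted, p = t(1 − f). Both t and f are assumptions; the documents give neither.

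| True rate t | Gate | f = 0 | f = 10% | f = 25% | f = 50% |
|---|---|---|---|---|---|
| 30% | 2 of 6 | 0.580 | 0.513 | 0.406 | 0.224 |
| 30% | 4 of 11 | 0.430 | 0.343 | 0.221 | 0.069 |
| 40% | 2 of 6 | 0.767 | 0.699 | 0.580 | 0.345 |
| 40% | 4 of 11 | 0.704 | 0.602 | 0.430 | 0.161 |

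The 35% to 25% case corresponds to f = 10/35 = 29%. The chance of triggering falls as f rises, so missed events act in one direction only.

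**The case against.** The strongest reply is that the plan can be read sensibly as it stands. The definition turns on when a toxicity occurs, not on when it is first detected. C2D1 is the next marked toxicity and DLT evaluation after C1D1, so it is naturally the end-of-Cycle-1 assessment, and an abnormality in a sample taken before any Cycle 2 dose must have arisen earlier. This is a fair reading, but the documents do not state it, and a stopping rule should not depend on it.

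Other points also stand:

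- The laboratory exception in 5.1 removes findings that are not clinically relevant. Section 8.4.1 treats laboratory values as adverse events only if they cause signs or symptoms or need therapy. Many transient, silent abnormalities may not qualify as DLTs at all.
- Symptomatic events can be found clinically, and persistent ones will show at C2D1 while accrual is held. Footnote 3 mentions other checks at the investigator's discretion, though only under the CBC.
- Serious events are reported within 24 hours (8.6) and the DSMC reviews quarterly (13.0). These are safeguards, but they are not the numeric gate.
- The phase 1 precedent is thin: hyperbilirubinemia appears in a pooled list from three patients, two of them at 126.6 mg/m², and was a serious event rather than a silent laboratory finding.

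A reader might infer that an ESK981-related abnormality will have cleared by C2D1, since 72 h is 72/9.9 = 7.3 half-lives at the overall day-15 mean. The documents do not support that step. Elimination of a drug is not resolution of its toxicity, and nothing in them shows how fast a Grade 3 chemistry value settles. Half-lives were also longer at some higher doses (13.9 h at 73.0 mg/m² gives 72/13.9 = 5.2). In Cohort B, nivolumab's stated half-life is 25 days (9.2), so exposure to it continues at day 29.

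**Conclusion.** The point holds as a gap in required observation and in attribution. No post-dose chemistry is required on days 2–28, the visit window permits such a draw without requiring it, and the status of a qualifying C2D1 result is not stated. What may be missed or counted inconsistently is narrow: a clinically relevant, Grade 3 or higher, asymptomatic chemistry abnormality that resolves before the C2D1 draw, or one first seen on or after day 29 and not assigned to Cycle 1.

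A reader might go further and infer that biochemical DLTs in general escape the gates, or that the gates lose about 20 percentage points of sensitivity. Neither follows. Symptomatic and persistent abnormalities can still be found, and the fall from 0.68 to 0.47 assumes both a 35% DLT rate and that 10 of those points are biochemical and uncounted. The direction of any loss, towards too few DLTs, is secure; its size is not known. This is a cheap improvement that should be made, not a defect that invalidates the gates.

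**What to change.** 1. In the Time and Events Table, add COMP to the weekly Cycle 1 blood draws that footnote 13 already requires.
2. In sections 5.1 and 11.3, state that a qualifying abnormality of Grade 3 or higher found at the C2D1 assessment, sampled before the first Cycle 2 dose, counts as a Cycle 1 DLT whichever day in its window the visit falls on. Keep the existing exception for laboratory abnormalities that are not clinically relevant.

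The first change lets the gate see chemistry during the window; the second removes the dependence on visit date. The cost is one footnote, one sentence in each section, and an extra tube at about three draws that already take place. Slightly more DLTs may be counted. The weekly draws can stay on their current days.

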5.2 Toxicities and Dosing Delays/Dose Modifications

Any patient who receives treatment on this protocol will be evaluable for toxicity. Each patient will be assessed for the development of toxicity according to the Time and Events Table (Section 6.1). Toxicity will be assessed according to the NCI Common Terminology Criteria for Adverse Events (CTCAE), version 4.03. Dose adjustments should be made according to the system showing the greatest degree of toxicity.

Table 5.2.1 Hematological Toxicities

Hematological Toxicity Dose Reductions for ESK981		
ANC ¹	Platelets	Action
≥ 1,500/ μ L or	>100,000/μL	None.
1000-1499/ μ L or	75,000-99,000/μL	
-1st Occurrence: Hold current dose until ANC ≥ 1,500/μL and platelets ≥ 100,000/μL. Do not replace missed doses. Restart next treatment at 1 dose lower.
 
-2nd Occurrence: Hold current dose until ANC ≥ 1,500/μL and platelets ≥ 100,000/μL. Do not replace missed doses. Restart next treatment at 1 dose lower if available or discontinue if not available
 
-3rd Occurrence: Discontinue protocol therapy.

500-999/ μ L or	50,000-74,000/μL	
-1st Occurrence: Hold current dose until ANC ≥ 1,500/μL and platelets ≥ 100,000/μL. Do not replace missed doses. Restart next treatment at 1 dose lower if available or discontinue if not available.
 
-2nd Occurrence: Hold current dose until ANC ≥ 1,500/μL and platelets ≥ 100,000/μL. Do not replace missed doses. Restart next treatment at 1 dose lower if available or discontinue if not available.
 
-3rd Occurrence: Discontinue protocol therapy.

<500/ μ L or	<50,000/μL	
-1st Occurrence: Hold current dose until ANC ≥ 1,500/μL and platelets ≥ 100,000/μL. Restart next treatment at 1 dose lower if available or discontinue if not available.
 
-2nd Occurrence: Discontinue protocol therapy.

¹Note: G-CSF (Filgrastim) may be added for low ANC on day of treatment *BEFORE* a dose reduction is instituted at treating physician's discretion. Neulasta® is NOT allowed.

Treatment-Emergent Non-hematological Toxicities: (EXCEPT non-clinically relevant/significant laboratory abnormalities):

NCI CTCAE Grade	ESK981	Nivolumab
1	No change from original starting dose	No change from original starting dose, supportive care as required
2	Hold until resolved to ≤ Grade 1, then reduce by 1 dose level if available or discontinue if not available	Hold until resolved to ≤ Grade 1, supportive care as required and then resume treatment
Second episode of grade 2 or 1 st episode of ≥ grade 3 toxicity	Hold until resolved to ≤ Grade 1, then reduce by 1 dose level if available or discontinue if not available	Discontinue treatment
Third episode of grade 2 or 2 nd episode of ≥ grade 3 toxicity	Discontinue treatment	

Note: The drug modifications for toxicity only apply to the drug the toxicity is attributed to (i.e. the offending drug), and the other drug could be continued without modification.

Note: Any drug holds for toxicity can continue for a maximum duration of 12 weeks. Beyond that, the offending drug shall be permanently discontinued. The other drug can be continued.

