Nivolumab (Opdivo) a PD-1 antibody, is FDA approved for the treatment of advanced renal cell carcinoma after disease progression on prior anti-angiogenic therapy. In the CHECKMATE-025 trial, nivolumab demonstrated improved overall survival compared with everolimus in the randomized clinical trial setting (25 months vs 19.6 months, HR 0.73, p-value 0.0018) [34].

ESK 981 in combination with anti-PD1 immunotherapy

VEGF inhibition in combination with immunotherapy in the form and anti-PD1 or anti-PD-L1 therapy has already been demonstrated in other drug combinations. Bevacizumab, an anti-VEGF therapy, in combination with atezolizumab (anti-PD-L1), was studied in ten patients with previously untreated metastatic RCC, and was well-tolerated. In this small cohort, there were 4 partial responses and 4 patients with stable disease [35]. A randomized multi-arm phase III clinical trial is currently ongoing evaluating the combination of lenvatinib, a multikinase inhibitor, with either everolimus or pembrolizumab compared with sunitinib in patients with advanced renal cell carcinoma (NCT02811861).

Given the superior activity of ESK981 compared to other small molecule VEGFR inhibitors especially potent inhibition of Tie-2 and additional autophagy inducing activity of ESK981, and the emerging clinical data on synergy between VEGFR inhibition and anti-PD1/L1 antibody immunotherapy, we propose a two-cohort phase II study. We first seek to evaluate the safety of ESK981 monotherapy in a safety cohort of 11 patients (Cohort A), after which accrual of Cohort B will begin, with a safety lead-in of six patients to establish a safe dose of ESK981 in combination with flat dose nivolumab at 480 mg IV. Subsequently, an expansion of Cohort B will be accrued to evaluate the clinical efficacy of the combination of ESK981 at the previously established safe dose in conjunction with nivolumab. Subjects in cohort A cannot cross-over into Cohort B.

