5.7 Patient Replacement

Patients who are not evaluable for objective response (as defined in Section 7.1.1) will be replaced.

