7.1.1 Definitions

Evaluable for toxicity. All patients will be evaluable for toxicity if they have received at least 1 dose of ESK981.

Evaluable for objective response. Only those patients who have measurable disease present at baseline, have received at least 2 cycle(s) of therapy, and have had their disease re-evaluated will be considered evaluable for response. These patients will have their

response classified according to the definitions stated below. (Note: Patients who exhibit objective disease progression prior to the end of cycle 2 will also be considered evaluable.)

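### The two DLT rules at 160 mg set no minimum Cycle 1 exposure, so a patient who took only a small part of the planned ESK981 counts as DLT-free at that dose

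*Combined protocol and SAP*

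**What the plan says.** All references are to the combined protocol and SAP.

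- **DLT definition (5.1).** "Dose limiting toxicity (DLT) will be defined as any Grade 3 or higher toxicity (as defined by CTCAE 4.03"), within the 28 days of Cycle 1. Laboratory abnormalities that are not clinically relevant are excepted. No hold, reduction, stop or missed-dose criterion is included.
- **The two rules at 160 mg (11.3).** In Cohort A, a DLT proportion above 30% means the planned combination dosing must be modified before Cohort B opens. In Cohort B, the dose drops one level on this condition: "If 2 or more DLTs occur in the first 6 patients of Cohort B". Section 1.3 gives the purpose: "with a safety lead-in of six patients to establish a safe dose of ESK981" in combination with nivolumab.
- **Dose modification (5.2).** For a first Grade 2 non-hematological toxicity attributed to ESK981: "Hold until resolved to ≤ Grade 1, then reduce by 1 dose level if available or discontinue if not available". A second episode brings another step down. The row headed "Third episode of grade 2" stops the drug. On length: "Any drug holds for toxicity can continue for a maximum duration of 12 weeks".
- **Who is counted (7.1.1).** "All patients will be evaluable for toxicity if they have received at least 1 dose of ESK981".
- **Who is replaced (5.7).** "Patients who are not evaluable for objective response (as defined in Section 7.1.1) will be replaced". No other ground for replacement is given.

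**The concern.** The dose tables take a patient off 160 mg at Grade 2, but the DLT rules react only at Grade 3. A hold may last 12 weeks, three times the length of the DLT window, so it can cover all the rest of Cycle 1. Since one dose is enough to be counted, a patient with little exposure to 160 mg enters the denominator as evidence that 160 mg is safe. The same happens to a patient who leaves in the first week for a reason unrelated to the drug. Section 5.7 would bring in a replacement for the response count, but nothing takes the early leaver out of the first six.

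What depends on this is the starting dose. The Cohort B rule chooses between 160 mg and 120 mg, and 36 − 6 = 30 further response-evaluable patients may then start at the chosen dose. If all six lead-in patients were held from Day 8 for Grade 2 toxicity, the rule would read 0 of 6 and 160 mg would stand. Pill diaries (5.1), weekly blood counts (6.1, note 13) and quarterly DSMC review (13.0) would show the problem, but no written rule acts on them.

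**Working it through.** The plan states no operating characteristics for either DLT rule, so there is no figure to reproduce.

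**1. Thresholds (11.3, 11.2).** Cohort A: 3/11 = 27.3% and 4/11 = 36.4%, so above 30% means 4 or more of 11. Cohort B: 2 or more of 6.

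**2. Exposure (5.1, 5.2).** Planned Cycle 1 is 5 doses × 4 weeks = 20 doses, and 20 × 160 = 3,200 mg. A full cycle at Level -1 is 20 × 120 = 2,400 mg, or 75%. Each path below is DLT-free as the plan stands:

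| Grade 2 toxicity and action | Cycle 1 ESK981 | Share |
|---|---|---|
| Day 8, held to Day 28 | 5 × 160 = 800 mg | 25% |
| Day 8, week 2 held, then 120 mg | 5 × 160 + 10 × 120 = 2,000 mg | 62.5% |
| Day 15, week 3 held, then 120 mg | 10 × 160 + 5 × 120 = 2,200 mg | 68.8% |
| Day 22, held to Day 28 | 15 × 160 = 2,400 mg | 75% |
| Day 8, one dose missed, then 120 mg | 5 × 160 + 14 × 120 = 2,480 mg | 77.5% |

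The first three fall below 2,400 mg. The last two do not.

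**3. Illustrative effect of toxicity-driven shortfalls.** Two inputs are assumed, because the documents give neither: p, the rate of Grade 3+ DLTs, and q, the share of patients with no DLT who fall below 2,400 mg because of ESK981-related toxicity. As written, each patient is an event with probability s = p, whatever q is. If shortfalls counted, s = p + q.

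- Cohort B: P(2 or more of 6) = 1 − (1 − s)^6 − 6s(1 − s)^5. At s = 0.15: 1 − 0.377 − 0.399 = 0.224. At s = 0.25: 1 − 0.178 − 0.356 = 0.466.
- Cohort A: P(4 or more of 11) = 1 − Σ C(11,k) s^k (1 − s)^(11−k), for k = 0 to 3. At s = 0.15: 0.069. At s = 0.25: 0.287.

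With p = 15%:

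| q (points) | Cohort B trips | Cohort A trips |
|---|---|---|
| 0 (equals the plan as written) | 0.22 | 0.07 |
| 5 | 0.35 | 0.16 |
| 10 | 0.47 | 0.29 |
| 20 | 0.68 | 0.57 |
| 30 | 0.84 | 0.81 |

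Other assumed DLT rates, moving from q = 0 to q = 10 points: at p = 10%, Cohort B goes from 0.11 to 0.35 and Cohort A from 0.02 to 0.16; at p = 5%, from 0.03 to 0.22 and from 0.002 to 0.07.

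**4. Illustrative effect of early departure for other reasons.** If one of the six leaves too soon to show a DLT, the rule in effect asks for 2 events among 5. At p = 15%: 1 − 0.85^5 − 5 × 0.15 × 0.85^4 = 1 − 0.444 − 0.392 = 0.16, against 0.22 with six fully observed patients.

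**5. Why such patients should be replaced and not just dropped.** Dropping two from Cohort A leaves 9. Since 3/9 = 33% exceeds 30%, the trigger falls from 4 events to 3, and P(3 or more of 9) at 15% is 0.14, against 0.07 for 4 or more of 11. Replacement keeps the denominators at 11 and 6.

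**The case against.** The best defence is that this is a deliberate design. Section 5.1.1 calls 160 mg a starting dose, two lower levels exist, and individual reductions are built in. On that view a Grade 3+ rule answers the safety question, and Grade 2 events are left to the dose tables. Counting more events also costs something: at q = 20 points the Cohort B starting dose would be lowered 68% of the time instead of 22%, possibly at some loss of efficacy. This defence stands against treating every Grade 2 reduction as a DLT. It does not explain why a patient with a quarter of the planned drug, or with one dose, should count as a full observation.

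Four stronger readings are tempting, and the documents do not support them.

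- **Filgrastim hides DLTs.** Footnote 1 to Table 5.2.1 allows it before a reduction, but Grade 3+ neutropenia treated with it is already a DLT unless considered not clinically relevant. Section 8.4.1, which makes an abnormal laboratory value that requires therapy an adverse event, favours counting it.
- **160 mg is poorly tolerated.** Phase 1 (1.2.4) reports that most events were Grade 1 or 2, but on daily dosing and with no Cycle 1 Grade 2 rate, so q cannot be read from it and may be zero.
- **Many patients will stop ESK981 for Grade 2 events in Cycle 1.** That takes three episodes within 28 days and is probably uncommon. Hold and reduction is the main route.
- **The response test is biased.** It is not. The gap concerns the choice of starting dose.

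**Conclusion.** The gap is real and can be read directly from Sections 5.1, 5.2, 5.7, 7.1.1 and 11.3: neither DLT rule at 160 mg requires any Cycle 1 exposure beyond one dose. What the documents fix is the size of the possible shortfall, down to 800 of 3,200 mg for a hold from Day 8 and less for an early leaver. They do not fix how often it happens. The trip probabilities therefore rest on assumed values of p and q and show sensitivity only; with no shortfalls there is no effect. A minimum exposure for DLT evaluability is standard practice, and its absence weakens a safety rule that sets the dose for most of Cohort B. The amendment is worth making before the rules are applied. The primary response analysis does not depend on it.

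**What to change.** Amend 5.1 and 11.3 for the two rules at 160 mg only (Cohort A and the first six of Cohort B):

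- (a) A patient without a DLT is DLT-evaluable only after at least 75% of planned Cycle 1 ESK981, that is, 2,400 mg or a full cycle at Level -1.
- (b) A patient below 2,400 mg because of ESK981-related toxicity of any grade counts as a DLT.
- (c) A patient below it for any other reason is replaced for the rule, in both cohorts, so the denominators stay 11 and 6.
- (d) Cycle 1 holds, reductions and G-CSF use are reported beside the DLT counts. This matters because the threshold does not catch every cut: the 2,480 mg path and the Day 22 hold at exactly 2,400 mg remain DLT-free.

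Leave the dose tables, footnote 1 and the Level -1 halting rule as they are, so that the added events can lead only to a dose modification and never to a halt.

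The cost is a few sentences. Pill diaries, concomitant medications and weekly Cycle 1 blood counts are already collected. The 160 mg rules will trip more often if toxicity-driven under-dosing is common, and replacement may slightly delay the lead-in. The 75% cut-off is a judgment, tied here to the protocol's own next dose level.
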